Alcohol use is inextricably linked to the HIV epidemic in fishing communities on Lake Victoria in Uganda, where HIV incidence among regular drinkers is 5 times higher than among non-drinkers.¹ Fishing communities are an HIV “hotspot;” HIV prevalence in fishing communities is estimated at >25%²⁻⁴ compared to the national prevalence of 7.3%.⁵ Prevalent alcohol consumption is also consistently reported across a range of studies with fisherfolk in Uganda^{3, 4, 6-8} and hazardous and harmful alcohol use, especially among *fisherfolk men*, is dramatically more prevalent (37%)⁶ than in the general population (5.8%).⁹ In our preliminary research Among the 61% of men who reported alcohol use, 60.2% had AUDIT scores (>7) indicative of hazardous/harmful alcohol use and 16% had AUDIT scores (>16) indicative of a high level of alcohol problems.⁶ Heavy alcohol use is especially problematic among individuals living with HIV as it leads to poor treatment outcomes¹⁰ and is associated with suboptimal antiretroviral (ART) adherence and engagement in care.¹¹⁻¹³

Like much of Uganda’s economy, fishing villages operate on a cash economy; workers get daily cash payments for their work but have limited mechanisms for savings due to a lack of access to traditional banking infrastructure. Poverty and stressful work conditions paired with easy access to alcohol and cash with no means of savings (i.e., access to banks, savings accounts) may be drivers of alcohol consumption among fisherfolk men.¹⁴ Moreover, frequent mobility and work responsibilities, a lack of social support, HIV stigma, and distance to the clinic have been shown to impede access to HIV care services among fisherfolk.^{15, 16} Given the unique context of heavy alcohol use and challenges with engaging fisherfolk men in HIV care, a combination intervention, which addresses structural as well as behavioral factors may be needed for this population.

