We propose to develop and pilot a brief combination intervention called *Kisoboka* which addresses the key drivers of alcohol use and barriers to HIV care engagement and ART adherence in this population. We address these multi-level factors in an intervention which combines behavioral components to promote behavior change with a structural component which changes the mode of work payments from cash to *mobile money*, to reduce “cash in the pocket,” and increase the accessibility of savings through mobile phone-based banking services. For the behavioral components, we will combine and adapt two efficacious alcohol interventions to the cultural and situational context of this population: a brief Motivational Interviewing (MI)-based intervention tested in Kenya¹⁷ and an intervention rooted in behavioral economics.¹⁸ The latter intervention focuses on increasing the extent to which individuals’ behavior is motivated by and consistent with their long-term goals such as saving money for the future—in which we will interweave the structural component of the intervention.

2. Specific objectives

Objective 1. Use formative research with fisherfolk men living with HIV and community stakeholders to adapt and develop a behavioral intervention *Kisoboka* (“*It is possible!*”) to reduce heavy alcohol use and promote engagement in HIV care and ART adherence among fisherfolk men living with HIV.

Objective 1b. Further refine the intervention through an initial pilot test with 15 participants examining feasibility and acceptability.

Objective 2. Pilot the *Kisoboka* intervention, randomizing to the *Kisoboka* intervention arm (n=80) or to the control arm (n=80, alcohol screening and referral). We will assess feasibility, acceptability, and preliminary estimates of the potential for the intervention, as compared to control, to decrease heavy drinking frequency and improve HIV care engagement and ART adherence through 6-month follow-up among this key population.

3. Methodology

3.1 Setting and population.

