We will conduct a stage 1b pilot randomized controlled trial of the intervention. As a pilot study, this study is not powered to detect differences in outcomes, but rather to obtain reliable estimates of effect sizes for a subsequent efficacy trial. However, for illustrative purposes we explore power assuming a small effect size ($d= 0.2$) which is consistent with most brief MI-based alcohol intervention study effect sizes^{17, 25-27} as well as care engagement interventions.²⁸⁻³² **We plan to enroll 160 participants in the pilot intervention trial** with 80 in each arm i.e., randomizing to the KISOBOKA intervention arm (n=80) or to the control arm (n=80, alcohol screening and referral). To be conservative we anticipate 25% attrition. This will provide 72% power to detect an intervention effect and 85% power to detect a study arm x time effect.

Sampling procedure for the randomized pilot intervention trial (n=160).

The participants recruited (based on the inclusion and exclusion criteria) from the Mildmay HIV clinics in Wakiso District will be requested to share the research assistant's contact details (phone numbers) with their potentially eligible friends. This snowball-sampling procedure will enable us to reach more participants in this hard-to-reach population. Those interested in participating in the study will contact the research assistant who will then take them through subsequent eligibility screening and recruitment procedures. This process will be repeated until the required sample is attained.

Randomization for stage 1b randomized pilot intervention trial.

Individual-level randomization with permuted block assignment balancing 1:1 will be used to create equal size groups for the two study arms. Blocks of 8 or 10 study-generated ID numbers will be created and randomly assigned to intervention or control. Once a participant is screened as eligible and attends an enrollment/baseline visit they will be assigned a study-generated ID number from the pre-randomized list which determined their study arm assignment.

Study variables

Dependent variables

Primary outcomes:

- Phosphatidylethanol (PEth) (alcohol biomarker, blood sample)
- AUDIT-C score¹⁹
- ART adherence³³

Secondary outcomes:

- HIV care engagement
- HIV viral load obtained from clinic records
- Frequency of heavy/binge drinking

Potential covariates

- Receipt of instrumental and emotional social support³⁴

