3.4 Measures

Unless otherwise noted all variables will be assessed at baseline and at follow-up, 3 and 6 months from baseline.

Primary alcohol outcome. We will use an **alcohol biomarker**: phosphatidylethanol (PEth) as the primary alcohol outcomes assessed at baseline and 6-month follow-up. PEth is a phospholipid which is formed only in the presence of alcohol and thus is highly specific.⁴⁷ PEth has shown good performance as a medium-term biomarker⁴⁸ and in controlled laboratory studies, correlated well with level of consumption (Spearman's $r = 0.6-0.8$).⁴⁹⁻⁵²

We will also use the AUDIT-C¹⁹ as another measure of hazardous alcohol use.

ART adherence: We will assess adherence to ART using the AIDS Clinical Trials Group Adherence measures (AACTG),⁵³ which includes recall questions about ARVs missed for the previous 4 days prior to the interview. It has demonstrated construct validity in Uganda and similar settings⁵⁴ and shows strong correlations with HIV VL⁵⁵ and moderate correlations with electronic adherence monitoring.⁵⁶

Measures and analysis for assessment of feasibility:

To inform a future larger randomized trial of the *KISOBOKA* intervention we follow Bowen et al.'s suggestions for conducting feasibility studies in preparation for larger RCTs²⁴ which includes assessing feasibility on the following dimensions: **acceptability, demand/use, implementation, and practicality**. We will document the number of intervention sessions participants attended which will speak to demand for/use of the intervention. To monitor implementation for the individual and group intervention sessions we will audio record intervention sessions and transcribe and code 20% of sessions to monitor intervention fidelity. Related to the practicality of the procedures, we will assess our retention rate through the 6-month follow-up to determine if we will need to develop additional retention procedures to maximize retention in a larger trial with a longer follow-up.

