3.5 Data management and analysis

Data management

Pre-testing: We have used many of these measures in our prior research and already have English and Luganda versions finalized. The remaining measures will be pre-tested with staff

and patients at the participating clinics before the stage 1a pilot intervention. At this stage, we will also pretest the entire follow-up questionnaire to assess the duration of the interview and if necessary, remove measures to reduce the interview length. The stage 1ab pilot intervention will then be used for further pretesting and subsequent revisions to ensure the comprehensibility of each item before the stage 1b trial.

Field editing of data: Except for PEth and Viral load data all data will be entered into the CAPI (computer assisted personal interview) program as it is collected during the assessment interviews. A research assistant will double enter PEth viral load test results into the data file identified only by study ID number.

Qualitative data: Audio recordings of all qualitative data will be transferred to an encrypted and password protected computer. Electronic audio recordings of individual and group counselling sessions will be transcribed within 6 months of the session and the audio recordings will be destroyed once the information from the recordings is written down and double-checked for accuracy.

Quantitative data: Data for the baseline, 3 and 6-month follow-up questionnaires will be entered in real-time using KoboCollect software (A CAPI program). Using the KoboCollect system also eliminates the possibility of any out-of-range responses and therefore, data cleaning is not necessary. Data collected using Kobo is easily exported into SAS and other statistical programs for analysis. A research assistant will double enter PEth test results and viral load test results extracted from clinic records, into the data file identified only by study ID number. Clinical record data will be double entered by the research assistant into this same data file upon receipt. The double entered data will be checked and any discrepancies will be corrected by double checking the clinic records, and by comparisons with the laboratory report.

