Data security: Data directly entered from the questionnaire interviews will be automatically encrypted and then uploaded onto a secure server. Only the PIs and data manager will have access to the server. No participant names will be stored in the database. All participants will be identified by a unique identifier, a random number assigned to them at the time of recruitment. In the event of loss of data or theft, all data files will be encrypted, and no outside user would be able to access the data. To ensure that no data that is collected is lost, encrypted data will be backed up on several sources: a separate server and copied to a secondary encrypted database used by the PI and biostatistician for additional processing.

Statistical Analysis Plan

A key objective of this study is to explore the effectiveness of the intervention vs. control and obtain effect size estimates to be used to design a future trial of this intervention. The primary outcomes are PEth scores, AUDIT-C score, and ARV adherence. Different statistical methods will be utilized depending on the type of outcome variable and whether minimum conditions for use of the methods are met. For example, log Gamma models may be used to analyze the difference in PEth scores between intervention and control groups given the expected distribution of PEth scores. An intent to treat approach will be utilized to determine analytic sample. Variables (except PEth which is measured at 2) will be measured at three time points (baseline, 3 and 6 months) so the dependency from the repeated measures must be considered. Information criterion such as AIC and BIC will be used to select the most appropriate covariance structure to address dependence. Generalized estimating equations (GEE) will be built to examine the intervention effect on our outcomes of interest across time points (baseline, 3 and 6 months), adjusting for repeated measurement, using a time*condition interaction term. Potential covariates for each adjusted model will be identified a priori from the literature and added to the model. Correlation matrices will be determined based on model fit. Statistically significant covariates will be retained in final fitted models using an alpha of 0.05.

4 Ethical considerations

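### Could the adjusted GEE models absorb part of the intervention effect, because covariates are kept at p < 0.05 and are not said to be baseline values?

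*Combined protocol and SAP*

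**What the plan says.** Section 3.5, Statistical Analysis Plan, fits GEE models over baseline, 3 and 6 months (PEth at baseline and 6 months only) and reads the intervention effect from a time-by-condition interaction. On adjustment it says "Potential covariates for each adjusted model will be identified a priori from the literature and added to the model", and then "Statistically significant covariates will be retained in final fitted models using an alpha of 0.05". Neither sentence gives the time point of the covariate values.

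The list of potential covariates in section 3.2 includes social support, dimensions of HIV stigma, delay discounting and motivation for HIV care engagement, again without a time point. Section 3.4 sets the measurement schedule: "Unless otherwise noted all variables will be assessed at baseline and at follow-up, 3 and 6 months from baseline". The pre-testing paragraph of section 3.5 qualifies this for the follow-up questionnaire, where the team may "remove measures to reduce the interview length".

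The purpose is estimation. The sample size paragraph in section 3.2 aims to "obtain reliable estimates of effect sizes for a subsequent efficacy trial", and section 3.5 to "obtain effect size estimates to be used to design a future trial of this intervention".

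**The concern.** Several listed covariates overlap with what the intervention works on. Session 1 gives motivational counselling on HIV care engagement, and motivation for care engagement is a candidate covariate. The group sessions name HIV stigma. The text messages try to make delayed rewards more salient, which points towards delay discounting. For stigma and social support there is also a two-step link: the background says "a lack of social support, HIV stigma, and distance to the clinic have been shown to impede access to HIV care services", and the intervention is described as one that "addresses the key drivers of alcohol use and barriers to HIV care engagement and ART adherence in this population".

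Follow-up values of these variables will exist by default, in the same long-format data that the GEE uses. A variable on the causal path predicts the outcome, so a p < 0.05 filter would tend to keep it. Adjusting for it would turn the total effect into a partial one, usually too small, in a pilot whose stated product is an effect size for planning a later trial.

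**Working it through.** **Inputs from the documents.** Effect 0.20 SD, 160 enrolled 1:1, 25% attrition (section 3.2); visits at 0, 3 and 6 months and a time-by-condition term (section 3.5). The plan gives no figure for covariate adjustment, so there is none to reproduce; its power percentages do not enter here.

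**Assumed inputs.** Intervention shift *a* in the covariate, covariate–outcome slope *b*, within-person correlation 0.5, continuous outcome with identity link, exchangeable GEE with robust standard errors, random dropout.

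**Step 1, size of the estimate's random error.** With 60 per arm left at 6 months, the variance of a change from baseline is 2 × (1 − 0.5) = 1 SD². The SE of the difference in change is √(1/60 + 1/60) = 0.183. Simulation with dropout and all available data gives 0.172 to 0.180.

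**Step 2, if follow-up values are entered.** The adjusted term estimates total − *a* × *b*. Simulation with 60 per arm, complete data and 2,000 trials per row:

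| *a* | *b* | *a* × *b* | Unadjusted | Baseline value entered | Follow-up value entered |
|---|---|---|---|---|---|
| 0.2 | 0.3 | 0.06 | 0.206 | 0.206 | 0.144 |
| 0.3 | 0.3 | 0.09 | 0.203 | 0.203 | 0.113 |
| 0.2 | 0.5 | 0.10 | 0.198 | 0.198 | 0.099 |
| 0.3 | 0.5 | 0.15 | 0.191 | 0.191 | 0.043 |

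The drop from the unadjusted to the last column is 0.062, 0.090, 0.099 and 0.148, as the formula predicts. The baseline column equals the unadjusted one.

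**Step 3, the same with the p < 0.05 rule and 25% dropout.** 4,000 runs per cell; the unadjusted model is used when the covariate is dropped:

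| *b* | Kept (%) | Loss, *a* = 0.1 | *a* = 0.2 | *a* = 0.3 |
|---|---|---|---|---|
| 0.05 | 18–19 | 0.0024 | 0.0044 | 0.0065 |
| 0.1 | 53–55 | 0.0072 | 0.0147 | 0.0228 |
| 0.2 | about 98 | 0.0200 | 0.0402 | 0.0588 |
| 0.3 | 100 | 0.0302 | 0.0590 | 0.0890 |
| 0.4 | 100 | 0.0409 | 0.0790 | 0.1184 |

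In SE units the range is 0.0024/0.176 = 0.01 to 0.1184/0.176 = 0.67. At weak slopes the rule limits the loss, because the covariate is usually dropped.

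**Step 4, if baseline values are entered.** A baseline main effect moves all of a person's visits by the same amount, so it has almost nothing to take from a term about change over time. Under the null, with 12 candidates of which 4 are prognostic (slope 0.2), 25% dropout and 20,000 runs, type I error is 5.39% after selection and 5.36% with the full list.

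**Step 5, would a fixed list do better?** With 4 non-prognostic baseline covariates forced in, the SD of the estimate is 0.1763, against 0.1761 unadjusted. A fixed list costs nothing, but steps 2 and 4 show no gain from it either.

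**The case for a change.** The strongest counter-argument is that SE measures random error, whereas this loss is systematic and, when the covariate moves in the helpful direction, always shrinks the effect. A later trial's sample size scales with 1/d². At shift 0.2 and slopes 0.1, 0.2 and 0.3, the inflation would be (0.20/0.1853)² = 1.2, (0.20/0.1598)² = 1.6 and (0.20/0.1410)² = 2.0. Choosing candidates in advance fixes which variables are considered, not which visit they come from.

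The algebra stands, and so does the silence on timing. Three things weaken the step from there to a fault in the plan.

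- The harm needs an act that the documents never describe. Measuring a variable again at follow-up is not a decision to adjust for it.
- The link to the primary outcomes is uneven. The background ties stigma and social support to access to care, and motivation concerns care engagement, a secondary outcome. Adherence could plausibly be affected; for PEth and AUDIT-C no passage says that these covariates predict them. Delay discounting is the likeliest alcohol-side candidate, but only by inference.
- The control arm also gets AUDIT-C feedback, a referral and a short talk on care and adherence, which may narrow the difference in motivation.

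The inflation factors also sit beside a pilot estimate with an approximate 95% interval of 0.20 ± 1.96 × 0.18, or −0.15 to 0.55. A later trial cannot safely be sized on that point estimate alone, whichever model supplies it.

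**Conclusion.** No change is needed. The one rule that the plan does state, retention at p < 0.05, leaves the planned time-by-condition estimate and its type I error essentially as they were when baseline values are used, so replacing it would bring no gain. What is left is an unstated time point for the covariates. Analysts of a randomised comparison would ordinarily use baseline values; writing that down is optional.

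If follow-up values were used instead, the loss would be 0.002 to 0.118 SD over the grid in step 3, always below one SE. At the steepest slope tried (0.5, in step 2) it reaches 0.148/0.183 = 0.81 SE. These sizes rest wholly on assumed shifts and slopes, which the documents do not give, and on a continuous outcome with three visits. They do not carry over directly to PEth, which has two visits and a possible log Gamma model, or to the 4-day recall of missed doses. On a logit scale, any prognostic covariate would also change the coefficient somewhat, as a matter of scale.
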